7.5.1 Emergency Unblinding of Treatment Assignment

The IXRS will be programmed to allow an Investigator to unblind subjects and to unmask drug identity. When the Investigator contacts the system to unblind a subject, he/she must provide the requested subject identifying information and confirm the necessity to unblind the subject. The Sponsor will not provide a disclosure envelope with the clinical supplies.

The Investigator may unblind a subject's treatment assignment only in the case of an emergency when immediate knowledge of the study treatment is essential for the appropriate clinical management or welfare of the subject.

The decision to unblind must be that of the Investigator or delegated treating physician. Authorization from the Sponsor (or designee) is not required. Whenever possible, the

Investigator is encouraged to discuss options with the Sponsor's blinded Medical Monitor or appropriate study personnel before unblinding the subject's treatment assignment so long as this incurs no delay. If this is impractical, the Investigator must notify the Sponsor and/or Sponsor's blinded Medical Monitor as soon as possible, but without revealing the treatment assignment of the unblinded subject, unless that information is important for the safety of subjects currently in the study. The date and reason for the unblinding must be recorded in the appropriate data collection tool.

8 ADVERSE EVENTS

8.1 Performing Adverse Event Assessments

The Investigator is responsible for promptly documenting and reporting all AEs observed during the study in the subject's eCRF. If the AE is "unexpected," the Investigator must report the AE immediately to Sponsor or its designee. In addition, certain AEs (as described in Section 8.9) are classified as "serious" and must be reported no later than 24 hours after the Investigator recognizes/classifies the event as an SAE to the Sponsor or its designee.

In the case of SAEs, the Investigator may discontinue the subject from treatment prematurely but should discuss with the blinded Medical Monitor beforehand where possible.

8.2 Adverse Event Definitions

The following definitions of terms are guided by the ICH, the US Code of Federal Regulations (21 Code of Federal Regulations 312.32) and EU Directive 2001/83/EC and are included herein.

An AE is any untoward medical occurrence associated with the use of a drug in humans, whether or not considered drug related. An AE (also referred to as an adverse experience) can be any unfavourable and unintended sign (e.g., an abnormal laboratory finding), symptom, or disease temporally associated with the use of a drug, without any judgment about causality. An AE can arise from any use of the drug (e.g., off-label use, use in combination with another drug) and from any route of administration, formulation, or dose, including an overdose.

Adverse events include, but are not limited to:

- Any symptom or condition not previously reported by the subject (medical history).
- An exacerbation of a pre-existing symptom or condition.
- A significant increase in frequency or intensity of a pre-existing episodic event or condition.
- A drug interaction.
- A condition first detected or diagnosed after study drug administration even though it may have been present prior to the start of the study.

An AE does not include:

- Medical or surgical procedures (e.g., surgery, endoscopy, tooth extraction, blood transfusion); the condition that leads to the procedure is an AE (e.g., bleeding oesophageal varices, dental caries).
- Overdose of either study drug or concurrent medication without any clinical signs or symptoms.

- Non-clinically significant abnormal laboratory values. (If accompanied by signs/symptoms, the signs or symptoms are considered an AE).

8.3 Pre-randomization Adverse Events

Adverse events that occur between the time subject signs the ICF for the study and the time when that subject is randomized will be summarized as medical history and not as an AE unless the event meets the definition of an SAE as defined in Section 8.9.

8.4 Severity

The Investigator must categorize the severity of each AE according to the following guidelines:

Mild: Associated with no limitation of usual activities or only slight discomfort; generally, not requiring alteration or cessation of study drug administration; and/or not needing therapeutic intervention.

Moderate: Associated with limitation of usual activities or significant discomfort; generally requiring alteration or cessation of study drug administration; and/or requiring therapeutic intervention.

Severe: Associated with inability of subject to carry out usual activities or very marked discomfort; considered to be life-threatening; resulting in significant disability or incapacity; and requiring therapeutic intervention.

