5.9 Stopping Criteria

5.9.1 Study Stopping Criteria

If any of the following events develop during the study, at any dose of UPB-101, and these events are considered by the Investigator and/or Sponsor to be at least probably related to the administration of UPB-101, an *ad hoc* SRC meeting will be called immediately to investigate the event and to provide a recommendation for stopping or continuing the study or modifying the protocol:

- One or more subjects develop an SAE.
- Two or more subjects in the same cohort develop severe non-serious AEs, independent of within or not within the same system-organ-class.
- One or more subjects develop elevated plasma concentrations of ALT or AST ≥ 3 -fold the ULN and elevated plasma concentrations of total bilirubin (TBL) ≥ 2 -fold the ULN which is confirmed by repeat testing at least 48 to 72 hours after the initial test.

If the SRC recommends modifying the protocol as a condition for restarting the study, a protocol amendment will be submitted to the relevant regulatory authorities and IEC.

Procedures required prior to restarting a halted study are listed in Section 5.11.

Dose Escalation Stopping Criteria

If any of the following events develop during the study, dose escalation will be halted and the SRC will review the event and make a recommendation to stop dose escalation and/or continue dosing with modifications:

- Two or more subjects administered UPB-101 have an elevated plasma concentration of ALT or AST $\geq 3 \times$ ULN that is considered by the Investigator and/or Sponsor related to the investigational product and is confirmed by repeat testing 48 to 72 hours after the initial test.
- Two or more subjects administered UPB-101 have an elevated plasma concentration of TBL $\geq 2 \times$ ULN that is considered by the Investigator and/or Sponsor related to the investigational product and is confirmed by repeat testing 48 to 72 hours after the initial test.
- For additional information on hepatic parameter abnormalities, refer to Appendix 1, Liver Safety Monitoring and Assessment.
- One or more subjects administered UPB-101 has prolongation of QTcF, defined as QTcF >500 ms or >60 ms change from Baseline, that, on multiple ECGs, persists for at least 30 minutes and is considered by the Investigator and/or Sponsor related to the investigational product.
- Pharmacokinetic Stopping Rules – see Section 5.10.

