8.5 Relationship

The relationship of each AE to the study drug administration will be assessed by the Investigator after careful consideration, and according to the following guidelines:

Definitely: A reaction that follows a reasonable temporal sequence from administration of study drug; that follows a known or expected response pattern to the study drug; it disappears or decreases on cessation or reduction in study drug dose; and/or it reappears or worsens when the study drug is administered.

Probably: A reaction that follows a reasonable temporal sequence from administration of study drug; that follows a known or expected response pattern to the study drug; and/or that could not be reasonably explained by other factors such as underlying disease, complications, concomitant drugs, or concurrent treatments.

Possibly: A reaction that follows a reasonable temporal sequence from administration of study drug; that follows a known or expected response pattern to the study drug, but that could reasonably have been produced by a number of other factors including underlying disease, complications, concomitant drugs, or concurrent treatments.

Not Related: A reaction for which sufficient data exist to indicate that the aetiology is unrelated to the study drug.

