8.9.1 Reporting of Serious Adverse Events

All SAEs or serious pre-treatment events that occur during the course of the study must be promptly reported by the Investigator to tranScrip. Deaths and AEs assessed as life-threatening are to be reported immediately and SAEs that meet other criteria are to be reported within 24 hours from the point in time when the Investigator becomes aware of the SAE. All SAEs must be reported whether or not they are considered causally related to UPB-101. SAE forms will be completed, and the information collected will include subject number, a narrative description of the event, and an assessment by the Investigator as to the intensity of the event, criteria of seriousness, and relationship to study drug. Follow-up information on the SAE may be requested by the Sponsor or Medical Monitor.

Contact Information:

If there are serious, unexpected adverse drug reactions associated with the use of study drug, the Sponsor will notify the appropriate regulatory agency and all participating investigators on an expedited basis. The local Institutional Review Board (IRB)/IEC will be promptly notified based on local regulations where required by the IRB/IEC of all serious, unexpected adverse drug reactions involving risk to human subjects.

All AEs, whether serious or not, will be described in the source documents and in the appropriate section of the eCRF. All AEs and SAEs, including those that worsen in intensity or outcome of event or frequency relative to baseline, that occur after signing the ICF until Day 225 / Final Visit, must be recorded. Adverse events that are ongoing at the time of treatment discontinuation should be followed for a minimum of 90days after the last dose of study drug or the Final Visit whichever is later.

Information to be reported in the description of each AE includes:

- A medical diagnosis of the event (if a medical diagnosis cannot be determined, a description of each sign or symptom characterizing the event should be recorded).
- The date of onset of the event.
- The date of resolution of the event, if applicable.
- Whether the event is serious or not (include criteria for seriousness).

- Medical history of the subject and concomitant medications.
- Details of any laboratory tests.
- Intensity of the event (refer to Section 8.4 for definitions).
- Relationship of the event to study treatment (refer to Section 8.5 for definitions).

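### Read literally, Protocol 8.4 makes every Severe AE a serious one, so no AE graded by it could count as severe non-serious under 5.9.1 (minor wording fix)

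*Protocol*

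**What the plan says.** Protocol Section 8.4 requires the Investigator to grade every AE as Mild, Moderate or Severe and describes the three categories as guidelines. Section 8.9.1 sends the intensity entry in each AE description back to 8.4 for its definitions.

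- **Mild** closes with "and/or not needing therapeutic intervention".
- **Moderate**, which covers limited activities or significant discomfort, closes with "generally requiring alteration or cessation of study drug administration; and/or requiring therapeutic intervention".
- **Severe** opens with loss of usual activities or very marked discomfort and then continues "considered to be life-threatening; resulting in significant disability or incapacity; and requiring therapeutic intervention".

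Under Section 8.9 an AE is serious if any one listed outcome applies. Life threat is one; significant incapacity, or substantial disruption of normal life functions, is another.

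The second criterion in Section 5.9.1 for calling an ad hoc Safety Review Committee (SRC) meeting is "Two or more subjects in the same cohort develop severe non-serious AEs, independent of within or not within the same system-organ-class". All three criteria apply only where "these events are considered by the Investigator and/or Sponsor to be at least probably related to the administration of UPB-101".

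The SAP tabulates AEs by severity (Section 10.12.2; Table 14.3.2.1.3 up to Week 24) and gives no general severity scale of its own. Section 10.12.1 derives a size-based grade for erythema and swelling only.

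**The concern.** Sections 8.4 and 5.9.1 do not fit together as worded. If the Severe clauses are cumulative, grading an event Severe already makes it serious, and the 5.9.1 criterion then asks for two subjects with a kind of event that the 8.4 scale cannot produce.

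Three things would follow at a site that applied the text literally:

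- Very marked discomfort without life threat or disability would be graded Moderate, and would appear as such in the severity tables for the primary safety endpoint.
- Such an event would not count towards the two-subject trigger.
- SAP 10.12.2 treats a worsening in severity as a new event. A Moderate event that progressed to very marked discomfort would keep its grade and create no new record.

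Nothing in the protocol tells a site which reading to use. The study has 3 to 5 sites and 6 active subjects per cohort, so different readings could make a few grades inconsistent, and a few grades are visible in tables of this size.

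**Working it through.** The plan states no figure on this point, so the check is one of logic.

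**1. Conjunctions in 8.4 and 8.5.** Five semicolon lists close with and or and/or. Four use and/or: Mild, Moderate, Definitely ("and/or it reappears or worsens when the study drug is administered") and Probably ("and/or that could not be reasonably explained by other factors such as underlying disease"). One, Severe, uses a plain and. The Possibly category is also a semicolon list, but it closes with a but-clause and reads cumulatively. The pattern therefore suggests a slip without proving one.

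**2. Features.** Let D = unable to do usual activities, or very marked discomfort; L = life-threatening; I = significant disability or incapacity; T = needs therapeutic intervention; O = any other route to seriousness in 8.9. Each is true or false, giving 2^5 = 32 combinations. From 8.9, an event is non-serious only when L, I and O are all false.

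**3. Combinations that are Severe and non-serious.**

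| Reading of Severe | Condition | Severe and non-serious |
|---|---|---|
| Literal 8.4 | D and L and I and T | 0 of 32 |
| Plain and/or | D or L or I or T | 3 of 32 (D; T; D with T) |
| Alternatives, intervention required | (D or L or I) and T | 1 of 32 (D with T) |
| Alternatives, intervention usual but not required | D or L or I | 2 of 32 (D; D with T) |

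The zero in the first row needs only L: life threat alone makes the event serious, so the result does not depend on how disability in 8.4 maps to incapacity in 8.9.

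**4. What the trigger would do under a workable definition.** Suppose each of the 6 active subjects in a cohort has probability p of a severe, non-serious, at least probably related AE, independently. The chance that two or more do is 1 − (1−p)^6 − 6p(1−p)^5.

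- p = 0.05: 1 − 0.7351 − 0.2321 = 3.3%
- p = 0.10: 1 − 0.5314 − 0.3543 = 11.4%
- p = 0.20: 1 − 0.2621 − 0.3932 = 34.5%
- p = 0.30: 1 − 0.1176 − 0.3025 = 58.0%

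For events graded by 8.4 read literally, p = 0 and the chance is 0. These values of p are assumptions; the documents give no rate of severe AEs. The list shows how the rule behaves and does not estimate what is lost.

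**The case against.** The strongest reply is that nobody would grade this way. Section 8.4 calls its categories guidelines, and the literal reading gives an absurd result: a life-threatening reaction that left no disability would not be Severe. Section 5.9.1 presupposes severe events that are not serious, so the intent can be recovered from the protocol. This largely stands, and it is why the point is minor. It does not remove the conflict, because grading by 8.4 is mandatory and no passage states the intended reading.

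A reader might go further and infer that the second 5.9.1 criterion can never be met by any event. The documents do not support that. Section 5.9.1 does not cite 8.4. Appendix 1 has the Investigator classify confirmed liver abnormalities as moderate or severe, and says that severe ones may, not must, be reported as SAEs. SAP 10.12.1 labels erythema or swelling above 10 cm as Severe whether or not it is serious. The zero applies to 8.4 grades read literally. Nor do the documents show that any site has under-graded an event.

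The consequence is also bounded. A 5.9.1 criterion calls a meeting and does not itself stop the study. Other routes remain:

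- One at least probably related SAE calls the same meeting. Section 8.9 already counts substantial disruption of normal life functions, and important medical events, as potentially serious.
- Unexpected AEs go to the Sponsor at once (8.1), and Principal Investigators must raise safety issues with the blinded Medical Monitor (5.7).
- The dose escalation criteria include any event posing an unacceptable risk to other subjects.
- The SRC meets before third doses in Cohorts 1 and 2, and all AEs are listed.

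These cover most of the ground, though not as a count. The unacceptable-risk criterion rests on judgement, and Cohort 4, dosed on Day 1 only, has no linked SRC meeting.

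**Conclusion.** The wording conflict is real and the practical gap is narrow. On a literal reading, 0 of 32 feature combinations are both Severe under 8.4 and non-serious under 8.9, so one of the three 5.9.1 criteria has no 8.4-graded event to count. The gap is mainly very marked discomfort without life threat or disability. To matter for the trigger, it would have to be at least probably related, occur in two subjects of one cohort, and be graded by someone reading the sentence literally. The effect on the severity tables cannot be derived from the documents.

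The conclusion assumes that the clauses are read as cumulative and that 8.4 supplies the grade used for 5.9.1. Both are natural on the text, but neither is certain in practice. The likeliest explanation is a slip for alternatives. It merits a minor correction because it touches an operative safety rule and costs one sentence.

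**What to change.** Reword Severe along these lines: *the subject is unable to perform usual activities or has very marked discomfort, or the event is life-threatening, or it results in significant disability or incapacity; therapeutic intervention is generally required.* Repeat it in the eCRF guidance. Changing the conjunction to and/or is not enough: a need for therapeutic intervention alone would then qualify as Severe while it also appears under Moderate.

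Some AEs will already have been graded. Day 225 falls 224 days after the first dose. A last visit on 31 October 2023 (day 304 of the year) puts the last first dose at day 304 − 224 = 80, or 21 March 2023, and at 26 March with the 5-day visit window. Both dates precede Version 9.0 of 31 March 2023. This assumes that the stated end date holds and that no later Cohort 5 is opened. On that timeline little dosing is left for the trigger to protect, and the gain is mostly consistent severity tables.

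If existing grades are checked, blinded Investigators should confirm all of them against the new definition before database lock. A query limited to Moderate grades could only move severity upward, and in a study whose Sponsor is unblinded throughout that selectivity is best avoided. The alternative is to leave existing grades alone.

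The cost is one sentence, matching eCRF text and, if chosen, one round of site queries. Some events may be graded higher, and the SRC trigger may fire slightly more often.

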8.5 Relationship

The relationship of each AE to the study drug administration will be assessed by the Investigator after careful consideration, and according to the following guidelines:

Definitely: A reaction that follows a reasonable temporal sequence from administration of study drug; that follows a known or expected response pattern to the study drug; it disappears or decreases on cessation or reduction in study drug dose; and/or it reappears or worsens when the study drug is administered.

Probably: A reaction that follows a reasonable temporal sequence from administration of study drug; that follows a known or expected response pattern to the study drug; and/or that could not be reasonably explained by other factors such as underlying disease, complications, concomitant drugs, or concurrent treatments.

Possibly: A reaction that follows a reasonable temporal sequence from administration of study drug; that follows a known or expected response pattern to the study drug, but that could reasonably have been produced by a number of other factors including underlying disease, complications, concomitant drugs, or concurrent treatments.

Not Related: A reaction for which sufficient data exist to indicate that the aetiology is unrelated to the study drug.

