These data provide the rationale for the parallel cohort design. For all cohorts, the projected single dose exposures are lower than the exposures that were found to be safe and well tolerated in Study 7266-CL-0001.

Table 1 Predicted Mean PK parameters After Single SC Administration UPB-101 Compared to the Maximal IV Dose of Completed Study 7266-CL-0001

Route	Single Dose				Fraction of Maximal SAD Exposure	
	Dose (mg)	Dose (mg/kg)	C_{max} ($\mu\text{g}/\text{mL}$)	AUC_{inf} (days· $\mu\text{g}/\text{mL}$)	C_{max} IV/ C_{max} SC	AUC_{inf} IV/ AUC_{inf} SC
SC	█	█	█	█	█	█
SC	█	█	█	█	█	█
SC	█	█	█	█	█	█
SC	█	█	█	█	█	█
IV	█	█	█	█		

AUC_{inf} =area under the concentration-time curve from the time of dosing extrapolated to time infinity; C_{max} =maximum observed concentration; IV=intravenous; PK=pharmacokinetic; SAD=single ascending dose; SC=subcutaneous.

Local Tolerability

All subjects enrolled in this study will receive █ mg or █ mg SC injections at each dosing visit depending upon to which cohort they are assigned. For example, subjects assigned to Cohort 1 (█ mg █) will received two █ mg SC injections at 2 separate injection sites at each dosing visit. The SC dose administered in the SAD study was █ mg/kg (█ mg) and was well-tolerated; no injection site reactions were reported. Therefore, no significant local skin reactions are anticipated in the current study.

Multiple Dose

[figure not shown]
The PK model described above was used to simulate multiple dose PK for the doses and dosing intervals to be administered in this study. Predicted PK parameters and predicted mean PK profiles after repeated SC administration of UPB-101 are shown in Table 2 and Figure 1, respectively. There is minimal accumulation after repeated administration, with close to steady state levels reached after 3 injection (for [REDACTED] regimen) or 2 injections (for [REDACTED] and [REDACTED] regimens). The predicted C_{max} and area under the concentration-time curve for one dosing interval (AUC_{tau}) in this study (at the highest dose of [REDACTED] mg SC) are [REDACTED]-fold and [REDACTED]-fold lower, respectively, when compared with the observed C_{max} and AUC_{inf} following administration of [REDACTED] mg/kg IV in Study 7266-CL-0001, a dose that was found to be safe and well- tolerated.

Table 2 Predicted Serum PK Parameters After Repeated SC Administration of UPB-101

Dose	Frequency	Number of doses	Multiple SC dose		
			Interval	C_{max} (µg/mL)	AUC_{tau} (days·µg/mL)

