### 10.12.2. *Adverse Events*

Adverse event (AE) data presentations will be produced for unsolicited adverse events that occur during the study.

All adverse events will be coded using MedDRA, Version 25.0.

Treatment emergent adverse events will be summarized over 2 distinct time periods within the study, from first dose of study treatment to Week 24, as well as from first dose of study treatment to Week 32 (i.e. over the entire study period).

Adverse events will be assigned to time periods according to the AE start and stop dates and times and dates/times of first dose of study treatment. Any adverse event with an onset date/time earlier than the date/time of first dose of study treatment will be classified as a pre-treatment adverse event. Any adverse event worsening in severity will be considered as a separate event, starting from the date/time of the updated severity.

Should any onset date for an adverse event be missing or only a partial date recorded (such that it cannot be determined if the event onset was prior to first dose of study treatment or not) then it will be assumed that the event is following first dose of study treatment, unless the adverse event stop date indicates otherwise.

If a subject experiences more than one adverse event with the same preferred term, that preferred term will be counted only once in summary presentations. It will be assigned the worst observed

severity and the strongest relationship to IMP among those events for the summaries in which those characteristics are considered.

Adverse Events of Special Interest (AESI) will be identified within the database as such. Additionally injection site reactions will be considered as AESIs.

An overall summary of adverse events will present the number of subjects with events and serious adverse events (also split by severity), number of subjects with adverse events and serious adverse events related to study treatment, the number of subjects with adverse events leading to discontinuation from study treatment or withdrawal from the study. This summary will be produced for adverse events occurring from first dose of study treatment to Week 24, and over the entire study period.

Additionally, each of the summaries below will be presented for the entire study period:

- Adverse Events by treatment group, System Organ Class (SOC) and Preferred Term (PT).
- Serious Adverse Events by treatment group, SOC and PT.
- Adverse Events by treatment group, SOC, PT and severity.

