14.3.2.1.2	Treatment Emergent Adverse Events by System Organ Class and Preferred Term up to Week 24 – Safety Population	X	
14.3.2.1.3	Treatment Emergent Adverse Events by System Organ Class, Preferred Term and Severity up to Week 24 – Safety Population	X	
14.3.2.1.4	Treatment Emergent Adverse Events Related to IMP by System Organ Class and Preferred Term up to Week 24 – Safety Population	X	
14.3.2.1.5	Treatment Emergent Adverse Events of Special Interest by System Organ Class and Preferred Term up to Week 24 – Safety Population	X	
14.3.2.1.6	Treatment Emergent Serious Adverse Events by System Organ Class and Preferred Term up to Week 24 – Safety Population	X	X
14.3.2.1.7	Treatment Emergent Adverse Events Leading to Discontinuation of Investigational Product by System Organ Class and Preferred Term up to Week 24 – Safety Population	X	

Table Number	Table Title	Final	Admin Analysis
14.3.2.1.8	Treatment Emergent Adverse Events Leading to Withdrawal from the Study by System Organ Class and Preferred Term up to Week 24 – Safety Population	X	X
14.3.2.2.1	Overall Summary of Treatment Emergent Adverse Events Over Entire Study Period – Safety Population	X	
14.3.2.2.2	Treatment Emergent Adverse Events by System Organ Class and Preferred Term Over Entire Study Period – Safety Population	X	
14.3.2.2.3	Treatment Emergent Adverse Events by System Organ Class, Preferred Term and Severity Over Entire Study Period – Safety Population	X	
14.3.2.2.4	Treatment Emergent Adverse Events Related to IMP by System Organ Class and Preferred Term Over Entire Study Period – Safety Population	X	
14.3.2.2.5	Treatment Emergent Adverse Events of Special Interest by System Organ Class and Preferred Term Over Entire Study Period – Safety Population	X	
14.3.2.2.6	Treatment Emergent Serious Adverse Events by System Organ Class and Preferred Term Over Entire Study Period – Safety Population	X	
14.3.3.1	Haematology Parameters Summary – Safety Population	X	
14.3.3.2	Haematology Parameters: Shift of Normal Range – Safety Population	X	
14.3.4.1	Biochemistry Parameters Summary – Safety Population	X	
14.3.4.2	Biochemistry Parameters: Shift of Normal Range – Safety Population	X	
14.3.5.1	Coagulation Parameters Summary – Safety Population	X	
14.3.5.2	Coagulation Parameters: Shift of Normal Range – Safety Population	X	
14.3.6	Urinalysis Parameters: Summary – Safety Population	X	
14.3.7	Vital Signs Parameters Summary – Safety Population	X	

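### Protocol 8.5 makes a known or expected response pattern a condition of *Possibly* related, so, read literally, a plausible new event that also has another possible cause fits none of the four categories

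*Protocol*

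**What the plan says.** Protocol 8.5 states that "The relationship of each AE to the study drug administration will be assessed by the Investigator after careful consideration", with four definitions offered as guidelines:

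- *Definitely*: reasonable timing; known or expected pattern; "it disappears or decreases on cessation or reduction in study drug dose; and/or it reappears or worsens when the study drug is administered".
- *Probably*: reasonable timing; known or expected pattern; "and/or that could not be reasonably explained by other factors such as underlying disease, complications, concomitant drugs, or concurrent treatments".
- *Possibly*: reasonable timing, and a reaction "that follows a known or expected response pattern to the study drug, but that could reasonably have been produced" by a number of other factors. There is no and/or.
- *Not Related*: "A reaction for which sufficient data exist to indicate that the aetiology is unrelated to the study drug".

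There is no unlikely, unassessable or residual level.

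SAP 10.12.2 uses the grading in its overall summary, which counts subjects with related AEs and related SAEs, and in a related-event summary by SOC and PT. Where a preferred term recurs in a subject, the SAP takes "the strongest relationship to IMP among those events for the summaries" that consider it. SAP 13.2 lists "Treatment Emergent Adverse Events Related to IMP by System Organ Class and Preferred Term up to Week 24" (Table 14.3.2.1.4) and the same table for the entire study period (14.3.2.2.4). The SAP text does not say which levels count as related. It has a rule for incomplete onset dates but none for a missing relationship.

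**The concern.** *Possibly* is normally where an event goes when the drug might be the cause but something else might be too. Here it is open only to events that already match a known or expected pattern. A new type of event with a competing explanation is shut out of *Possibly* by the pattern condition and out of *Not Related* by the evidence condition.

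The setting makes such events plausible. Protocol 1.4.1 reports one completed human study, at single doses in healthy volunteers. This trial gives repeated doses to subjects with asthma on background medication, who will sometimes have another explanation for an event.

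The protocol also expects unexpected reactions: 8.9 defines unexpectedness by absence from the Investigator's Brochure, and 8.9.6 requires reports of suspected reactions that are serious and unexpected. A scale whose lowest related level demands a known or expected pattern does not fit that provision. At stake are the related-event outputs and the reporting that turns on relationship, such as post-study SAEs under 8.9.4.

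**Working it through.** The plan states no figure to reproduce. The check is logical, with one small calculation for scale.

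**Test event.** Timing reasonable (T = yes); known or expected pattern (K = no); other factors could explain it (O = yes); positive dechallenge (D = no); positive rechallenge (R = no); sufficient data that it is unrelated (U = no).

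**Fixed conditions.** *Possibly* = T and K and O. Since K = no, it fails. *Not Related* = U. Since U = no, it fails. Neither depends on how and/or is read.

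**The and/or in the upper two levels** can be read in four ways:

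| Reading | *Definitely* | *Probably* | Test event |
|---|---|---|---|
| 1. Timing plus at least one other item | T and (K or D or R) | T and (K or not O) | No category |
| 2. Timing and pattern both required | T and K and (D or R) | T and K and not O | No category |
| 3. Timing and pattern, or timing and last item | (T and K and D) or (T and R) | (T and K) or (T and not O) | No category |
| 4. Any single item is enough | T or K or D or R | T or K or not O | *Definitely* and *Probably* |

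Reading 4 is not credible: timing alone would earn *Definitely*, above *Possibly*, which asks for more. On the three sensible readings the event has no category.

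**Does the gap depend on the other cause?** Set O = no and keep K = no. The event then reaches *Probably* under readings 1 and 3, but still has no category under reading 2. So the gap for a new event with a competing cause is common to all three sensible readings.

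**After the repair.** If the pattern supports *Possibly* but is not required, the condition becomes T and O. The test event meets it however the upper two levels are read.

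**Weight of one subject.** Protocol 9.2 gives 6 active subjects per cohort. One subject moving between related and not related changes the related-event rate by:

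- one cohort: 1/6 = 16.7 percentage points;
- Part A, 3 × 6 = 18 active: 1/18 = 5.6 points;
- all five cohorts, 5 × 6 = 30 active: 1/30 = 3.3 points.

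**The case against.** **The definitions are guidelines.** An investigator may still choose *Possibly* on plausible timing and a competing explanation. This stands: the gap is in the text, and how often it affects a grading is unknown. But a grading reached that way departs from the written condition.

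**Expected is broader than known.** Expectations can come from the AESIs in Protocol 8.7, the toxicology and theoretical risks in Table 3, and the approved product of similar mechanism in 1.8.3. The prior study's detailed results are redacted and the Investigator's Brochure is not to hand. This also stands, and it narrows the gap by an unknown amount. The remark in Protocol 1.7 that "no injection site reactions were reported" adds little, because such reactions are a named AESI anyway.

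**Stronger readings that the documents do not support.** A reader might infer any of these:

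- *Events are lost from the primary safety evaluation.* They are not. The primary endpoints are AEs and SAEs whatever their cause, and all AEs are tabulated and listed.
- *Investigators will default to Not Related, or will differ by site.* Nothing says so, and the literal wording of *Not Related* bars that default.
- *The comparison with placebo is biased.* Investigators are blinded, so the wording gives no evident reason for gradings to differ by arm.
- *A definite number of events is affected.* No document gives the expected number of events or the share falling in the gap.

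**Other safeguards exist.** SAEs during the study are reported regardless of relationship (8.9.1), and a blinded Medical Monitor supports Sponsor causality (7.5). These limit the consequences but do not supply the missing category.

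**Unseen material.** The SAP Section 14 shells and the eCRF guidance were not available and may define related. That bears on the SAP sentence proposed below, not on the wording of 8.5.

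**Conclusion.** The gap holds on every sensible reading of Protocol 8.5. It is a defect in a stated rule, not missing detail. Its reach is limited to the related counts in the overall AE summary, Tables 14.3.2.1.4 and 14.3.2.2.4, and reporting that depends on relationship. These outputs are descriptive.

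The number of events and the direction in which they would be graded cannot be derived. The only size that can be stated is the leverage of one subject: 16.7 points in a cohort, falling to 5.6 across Part A and 3.3 across five cohorts. The conclusion assumes that *Possibly* is applied as written and that one item alone does not satisfy *Definitely* or *Probably*. The wording should be changed because the repair is cheap and safety is the primary objective.

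**What to change.** 1. **Protocol 8.5.** Reword *Possibly* so that the response pattern is supportive and not mandatory: reasonable timing, and/or a known or expected pattern as in *Probably*, with another possible cause. Say explicitly that the pattern is not required, because and/or alone can be read as keeping it (reading 2). Keep the Investigator's judgement of whether a drug cause is plausible, so that timing plus any background illness does not count automatically.
2. **SAP 10.12.2.** State that related means possibly, probably or definitely, and say how a missing relationship is handled.
3. **Existing gradings.** If the wording changes during the study, have the Investigators and the blinded Medical Monitor review all relationship gradings under the blind before database lock. Reviewing only those graded *Not Related* could only raise the related count.
4. **Dependent passages.** Reconcile Protocol 5.9.1 (at least probably related, and the escalation criteria that use related), 8.9.4 and 8.9.6 with the revised scale. No change to any stopping criterion is proposed here.

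The cost is a line in the protocol and eCRF guidance, a sentence or two in the SAP, and one blinded review. The downside is that a few more background events may be counted as possibly related.
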